**Table 3: Flotetuzumab Ramp, Induction, and Consolidation Dosing Guidelines**

Ramp + Induction			
Cycle	Weeks	Days	Dose (ng/kg/day)
1	1	Day 1	30
		Day 2	60
		Day 3	100
		Day 4	200
		Day 5	300
		Day 6	400
		Day 7	500
	2	Days 8-14	500
	3	Days 15-21	500
	4	Days 22-28	500
Induction/Consolidation			
2	1-4	Days 1-28	500

Table provided for dosing guidelines. Actual dosing may be altered as clinically indicated.'

### 5.2.2 Cycle 2 Flotetuzumab Consolidation

Patients meeting the primary endpoint of CR/CRi and patients with PR/SD (with permission of the investigator) will receive Cycle 2 flotetuzumab pre-medications and a continuous infusion of flotetuzumab (Tables 1 & 3), beginning within 2 weeks of completing Cycle 1.

- Patients will be admitted to the hospital and pre-medications administered on Day 1.
  - If patients have been off flotetuzumab for >72 hours, then the dose escalation ramp will begin on Day 1 and will consist of continuous ramp infusion of flotetuzumab starting at 30 ng/kg/day with increasing dose over 7 days to a target dose of 500 ng/kg/day. Patients will then continue on flotetuzumab for additional 21 days at target dose of 500 ng/kg/day (28 days total).
  - If patients have been off flotetuzumab ≤72 hours, then patients will receive flotetuzumab dosed at 500 ng/kg/day continuous infusion for a total of 4 weeks (28 days).
- At the end of Cycle 2 (Day 28), patients will undergo bone marrow biopsy for disease response assessment and correlative studies, and proceed to the follow-up phase of the study.

### 5.2.3 Donor Lymphocyte Infusion (DLI)

Patients with available donor cells may receive a donor lymphocyte infusion during Cycle 1 and/or Cycle 2 (if given) at the discretion of the investigator and the treating physician.

- DLI should be administered on or after Day 8 of Cycle 1 and/or Cycle 2

- Cell dose of DLI will vary depending on donor source at the discretion of the treating physician and according to institutional practices:
  - For matched unrelated donors and matched related donors DLI containing a range of  $0.5 \times 10^7$  to  $1.0 \times 10^8$  CD3+ cells/kg will be administered.
  - For haploidentical and mismatched donors DLI containing a range of  $0.5 \times 10^6$  to  $1.0 \times 10^7$  CD3+ cells/kg will be administered.

### 5.3 Response Assessments

Bone Marrow Biopsy (BM Bx) will be performed at the following timepoints for disease assessments and correlative assessments:

- Screening/Baseline BM Bx: performed prior to starting on treatment.
- Cycle 1 D14 (+/- 3 days) BM Bx mid-Cycle 1 (correlative assessments only, no disease response assessment, collected at PI's discretion only).
- Cycle 1 D28 (+/- 3 days) BM Bx following completion of Cycle 1.
- Cycle 2 D28 (+/- 3 days) BM Bx following completion of Cycle 2.
- Final BM Bx performed at the time of suspected disease relapse or progression.

Responses will be assessed via IWG Criteria (Table 2).

See Section 7.0 for additional details regarding bone marrow biopsy schedule and correlative assessments.

### 5.4 Safety Assessments

Safety assessments will be performed on an ongoing, continual basis to monitor for any AEs. Additionally, formal GVHD assessments will be performed at baseline, on C1 D1 prior to flotetuzumab dose, C1D28; for patients receiving DLI, formal GVHD assessments will be performed weekly following DLI and during follow up.

### 5.5 Definitions of Evaluability

Endpoint	To be evaluable for this endpoint, a patient must...
Efficacy (CR and CRi, C1D28 assessment)	Have completed all Cycle 1 infusions of flotetuzumab (or discontinued treatment due to drug toxicity or disease progression). Patients who are not evaluable for the primary objective will be replaced.
Efficacy (CR and CRi, C2D28 assessment)	Have completed all Cycle 1 and 2 infusions of flotetuzumab (or discontinued treatment due to drug toxicity or disease progression) and undergone C2D28 disease assessment
Efficacy (ORR defined as PR or greater)	Have completed all Cycle 1 infusions of flotetuzumab (or discontinued treatment due to

Efficacy (MLFS rate)	drug toxicity or progression) and undergone C2D28 disease assessment (or C1D28 assessment for patients who only received Cycle 1 treatment).
Efficacy (PR rate)	
Efficacy (SD rate)	
Efficacy (PFS)	
Efficacy (OS)	Have undergone any period of infusion of flotetuzumab
Safety and tolerability (AEs by CTCAE)	
Safety and tolerability (CRS and neurotoxicity by ASTCT)	
Safety and tolerability (acute GVHD by MAGIC criteria)	
Safety and tolerability (chronic GVHD by NIH severity score)	

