**6.4.3 Dose Delays and Modifications for aGVHD and cGVHD**

***Table 7: Dose Delays and Modifications for aGVHD***

MAGIC Grade I GVHD	The presence of new or worsening MAGIC Grade I GVHD should warrant standard of care therapies for commensurate GVHD level and does not require any dose modifications to the flotetuzumab.
---------------------------	--

MAGIC Grade II GVHD	The presence of new or worsening MAGIC Grade II GVHD should warrant standard of care therapies for commensurate GVHD and the does not require any dose modifications to the flotetuzumab. Persistent Grade II GVHD not improving with SOC interventions and supportive care within 24-48 hours requires a 25-50% dose reduction in flotetuzumab with continued SOC interventions, supportive care and continued monitoring of aGVHD severity. Uptitration of flotetuzumab to target dose may be attempted as per CRS protocol upon improvement of GVHD Grade to Grade I or better. However, persistent Grade II GVHD not improving with SOC interventions and with 25-50% dose reduction after 48-72 hours requires an immediate hold of flotetuzumab. Reinitiation of flotetuzumab with resolution of GVHD severity to Grade I or better can be attempted, resuming at 25-50% of the target dose and uptitration as per CRS protocol.
MAGIC Grade III GVHD	The presence of MAGIC Grade III GVHD should warrant standard of care therapies for commensurate GVHD and requires immediate hold of flotetuzumab. SOC interventions and supportive cares should be continued with daily assessment of GVHD Grade. Reinitiation of flotetuzumab with resolution of GVHD severity to Grade I or better can be attempted, resuming at 25-50% of the target dose and uptitration as per CRS protocol.
MAGIC Grade IV GVHD	The presence of MAGIC Grade IV GVHD should warrant standard of care therapies for commensurate GVHD and requires immediate hold of flotetuzumab. SOC interventions and supportive cares should be continued with daily assessment of aGVHD Grade. Reinitiation of flotetuzumab should not be attempted.

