### 11.3 Sample Size Estimate

Twenty-five evaluable patients will be enrolled for this study. Assuming a single treatment arm compared to historical controls treated with chemotherapy alone or HMA monotherapy using a dichotomous endpoint of CR/CRi vs not CR/CRi (as defined by the Primary Endpoint, as above), based on Simon's Minimax two-stage design, we estimate a sample size of 25 patients would provide 80% power (alpha 0.05) to detect a difference between a 10% CR/CRi rate in historical controls treated with chemotherapy or hypomethylating agents alone (10, 11) compared to 30% CR/CRi rate in the treatment arm (effect size 20%).

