### 11.5 Safety monitoring and determination of excess toxicity

To minimize risk to patients on study, we will perform interval analyses to determine if excess treatment-associated toxicity is observed during the trial. Toxicity may occur due to treatment with flotetuzumab, DLI administration, or unknown factors. Since GVHD may be an expected result of DLI, there will be separate stopping rules for excess non-GVHD toxicity and for GVHD toxicity.

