#### 11.5.1 Excess non-GVHD toxicity

Excess non-GVHD toxicity will be defined as a combined incidence of > 20% of any of the following:

- $\geq$  Grade 3 non-hematologic AE at least possibly attributable to protocol treatment, with the following exceptions:
  - Grade 3 fatigue, asthenia, fever, constipation or anorexia (if anorexia does not result in hospitalization, tube-feeding or use of total parenteral nutrition [TPN])
  - Grade 3 nausea, vomiting or diarrhea not requiring tube feeding, TPN, or requiring or prolonging hospitalization
  - Infection, bleeding, or other expected direct complications of cytopenias due to active underlying leukemia
  - Grade 3 infusion reaction including CRS, if successfully managed clinically and resolves within 7 days without end-organ damage
  - Grade 3 or 4 isolated electrolyte abnormalities that last < 72 hours

- Grade 4 neutropenia or thrombocytopenia lasting  $\geq 42$  days from the start of the cycle in the absence of MDS/AML
- Evidence of drug-induced liver injury based on presence of any of the following abnormalities without an alternate explanation:
  - ALT or AST  $>8x$  ULN
  - ALT or AST  $>5x$  ULN for more than 2 weeks
  - ALT or AST  $>3x$  ULN and (TBL  $>2x$ ULN or INR  $>1.5$ )
  - ALT or AST  $>3x$  ULN with the appearance of fatigue, nausea, vomiting, right upper quadrant pain or tenderness, fever, rash, and/or eosinophilia ( $>5\%$ )

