**11.7 Statistical analyses**

The data will be analyzed in both intent-to-treat (ITT) and per-protocol (PP) approaches. The ITT cohort will include all patients who have received at least one dose of flotetuzumab. The PP cohort will only include evaluable patients. Patients who withdraw before completing Cycle 1 for a reason unrelated to drug toxicity will not be evaluable for the primary objective and will be replaced. The data analyses will be descriptive in nature. Demographic and clinical characteristics of the sample, as well as response to treatment, and loss to follow up will be summarized using descriptive statistics. The CR rate, overall response rate, PR rate, SD rate, morphologic leukemia-free state (MLFS) rate, and AEs that occur during flotetuzumab monotherapy and their 90% confidence intervals will be presented. Rate of CR, overall response rate, PR rate, SSD rate, MLFS rate, and AEs with subsequent treatment will also be documented with exact 90% confidence intervals. Overall survival (OS) and progression-free survival (PFS) will be described using Kaplan-Meier product limit method.

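### Sections 5.5, 11.7 and 11.8 do not say whether stopping Cycle 1 for GVHD after DLI counts as drug toxicity, so a non-responding failure of the regimen can be replaced in the evaluable set

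*Combined protocol and SAP*

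**What the plan says.** Three sections of the protocol define who counts for the primary endpoint.

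- Section 5.5, primary efficacy row: the patient must have completed all Cycle 1 infusions, with this exception and consequence: "or discontinued treatment due to drug toxicity or disease progression). Patients who are not evaluable for the primary objective will be replaced".
- Section 11.7: "Patients who withdraw before completing Cycle 1 for a reason unrelated to drug toxicity will not be evaluable" and will be replaced. Progression is not mentioned. The per-protocol (PP) cohort holds evaluable patients only; the ITT cohort holds everyone dosed.
- Section 11.8: the efficacy analysis takes patients who complete a cycle, plus those who leave Cycle 1 for a reason at least possibly related to drug toxicity. Progression is again absent.

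None of these mentions DLI or GVHD, and drug toxicity is not defined. Section 5.2.3 allows DLI on or after Day 8 of Cycle 1. Table 7 (acute GVHD, Grade IV) and Table 8 (severe chronic GVHD) both direct a hold and then state: "Reinitiation of flotetuzumab should not be attempted".

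The safety text separates the possible causes. Section 11.5: "Toxicity may occur due to treatment with flotetuzumab, DLI administration, or unknown factors". Section 11.5.1 counts events "at least possibly attributable to protocol treatment". Section 13.0 calls flotetuzumab the study drug and names DLI-associated events separately.

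On the design, Section 11.3 plans for 25 evaluable patients: "we estimate a sample size of 25 patients would provide 80% power (alpha 0.05". The null is "a 10% CR/CRi rate in historical controls treated with chemotherapy or hypomethylating agents alone" and the target is 30%. Section 11.4 counts all treated patients at stage 1, including withdrawals.

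**The concern.** The trial tests flotetuzumab with optional DLI. A patient who receives DLI in Cycle 1, develops GVHD that ends flotetuzumab and has no response is a failure of that regimen. Whether the patient counts in the 25 evaluable turns on a term the plan does not define. The safety sections had a wider term available, protocol treatment, and the efficacy sections do not use it, so a flotetuzumab-only reading is plausible.

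The three rules can also class one patient differently. Suppose GVHD is judged mainly due to DLI but flotetuzumab cannot be ruled out. Section 11.8 keeps this patient. Section 5.5, which requires the stop to be due to drug toxicity, may not.

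What is at stake is an upward bias in the evaluable-set CR/CRi rate and some loss of control over the type I error of the final rule. The classification is a judgement made in an open-label trial, and the plan sets no time by which it must be fixed.

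**Working it through.** **Inputs.** Null rate 10%, target 30%, N = 25, alpha 0.05, power 80% (Section 11.3). Continue if at least 2 of 15 respond (Section 11.4). Success if at least 6 respond by the end of the study. This is the Appendix I wording; Section 11.4 ties the 6 to the cohort of 15. The check uses 6 of 25.

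**Step 1: reproduce the design.** With X1 ~ Bin(15, p) and X2 ~ Bin(10, p),

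P(success) = sum over x from 2 to 15 of P(X1 = x) × P(X2 ≥ 6 − x).

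At p = 0.10 the terms for x = 2, 3, 4 and 5 are
0.2669 × 0.0128 + 0.1285 × 0.0702 + 0.0428 × 0.2639 + 0.0105 × 0.6513.
Adding P(X1 ≥ 6) = 0.0022 gives 0.0328. At p = 0.30 the same sum is 0.802. The early-stop probability P(X1 ≤ 1) is 0.549 at 10% and 0.035 at 30%. The stated design reproduces.

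**Step 2: replace such patients.** Let q be the share of treated patients who stop Cycle 1 for GVHD, do not respond, and are replaced. If the response rate in all treated patients is p, the rate in the evaluable set is p/(1 − q). Put 0.10/(1 − q) into the step 1 formula:

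| q (assumed) | Evaluable-set rate | Type I error |
|---|---|---|
| 0 | 10.0% | 3.3% |
| 5% | 10.5% | 4.1% |
| 8% | 10.9% | 4.7% |
| 10% | 11.1% | 5.1% |
| 12% | 11.4% | 5.6% |
| 15% | 11.8% | 6.4% |
| 20% | 12.5% | 8.2% |

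The 5% limit is reached when the evaluable-set rate is 11.05%, that is q = 1 − 0.10/0.1105 = 9.5%.

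**Step 3: keep all treated patients at stage 1, as Section 11.4 says.** Among 15 treated, let x respond and d be later replaced (multinomial with probabilities 0.10, q and 0.90 − q). The trial continues if x ≥ 2, and 10 + d further evaluable patients then respond at rate 0.10/(1 − q). Type I error is 4.6% at q = 8% and 5.4% at q = 12%, slightly below the table.

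**Step 4: a concrete case.** Section 11.7 plans 90% intervals. The exact limits for 6 of n are the 5% quantile of Beta(6, n − 5) and the 95% quantile of Beta(7, n − 6).

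- 6/25 = 24.0%, interval 11.0% to 42.0%.
- With three replaced non-responders restored, 6/28 = 21.4%, interval 9.8% to 38.0%.

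The lower limit moves from above the 10% null to below it.

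**The case against.** **The text can be read to keep these patients.** A reader might infer that Section 5.5 settles the matter and makes a DLI-related GVHD stop non-evaluable. It does not. Drug toxicity is undefined, and Section 11.8 keeps stops at least possibly related to it. Section 6.4 says flotetuzumab may exacerbate GVHD, and DLI is given during the infusion, so flotetuzumab will often be hard to rule out. The contrast with Section 11.5.1 is also limited, because that section defines non-GVHD toxicity. This stands: the point is an ambiguity, not a stated exclusion.

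**They do not leave every denominator.** They remain in the ITT cohort and in the Section 11.4 stage 1 cohort. This stands too, but the plan does not say whether ITT or PP governs the final decision, and the sample size is counted in evaluable patients.

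**The size is unknown.** A reader might infer that alpha exceeds 5%, by multiplying the 25% severe-GVHD figure in Section 11.6 by the 50–70% of patients implied to be able to receive DLI in Section 1.1.3. That gives q = 12.5–17.5% and a type I error of 5.7–7.3%. The documents do not support this product. The 25% is a monitoring threshold for all treated patients over all treatment. The DLI figure comes from practice with chemotherapy followed by DLI, and the plan states no Cycle 1 uptake. Even on those figures, if half the events fell in Cycle 1, q would be 6.25–8.75% and the error 4.3–4.8%. Table 7 also allows a restart after Grade III improves, so not every hold is a final stop. A replaced responder would bias the rate the other way.

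**Outcome-aware attribution.** A reader might infer that causes would be assigned with the response known. The documents do not say so; the only Cycle 1 response marrow is at Day 28. What remains is that no deadline for attribution is set.

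**Conclusion.** The point holds as a gap and inconsistency in the evaluability rules. On a flotetuzumab-only reading, which Sections 11.5 and 13.0 make plausible, a non-responder who stops Cycle 1 for DLI-attributed GVHD is replaced, and the evaluable-set CR/CRi rate is inflated by the factor 1/(1 − q).

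The effect on type I error is modest and conditional. The design has slack (3.3% attained against 5% allowed), which absorbs the effect up to about q = 9.5%. This assumes that every affected patient is a non-responder, that all are replaced, and that the evaluable set governs the decision. The documents supply no value for q, so a breach of 5% is a possibility under an assumption, not a finding. The change should be made because the gap is foreseeable, the direction of bias for non-responders is clear, and the remedy is cheap.

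**What to change.** Use one rule in Sections 5.5, 11.7 and 11.8: a patient who does not complete Cycle 1 remains evaluable if the stop was for toxicity at least possibly related to protocol treatment (flotetuzumab or DLI), including GVHD, or for disease progression. State that these patients are not replaced. Score them by the C1D28 marrow if it was done, and otherwise as not CR/CRi.

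Then name the single population that governs both the stage 1 and final decisions, and align Section 11.4 and Appendix I with it. At present Section 11.4 counts all treated patients at stage 1, while Appendix I mentions only withdrawals unrelated to drug toxicity. The two also differ on whether the 6 responses refer to the first 15 patients or to the end of the study.

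The cost is a few wording changes in an amendment. The observed rate may be slightly lower, and fewer replacement patients are enrolled. If every dosed patient counts and none is replaced, the design keeps its 3.3% type I error and 80.2% power, with 10% and 30% read as rates among treated patients. No treatment rule changes.

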Description of Sites/ Facilities Enrolling:	This is a single institution open label study being conducted at Washington University in St. Louis.
Description of Study Intervention:	Phase 2, single-center, single-arm, open-label trial design evaluating the efficacy of flotetuzumab for the indication of relapsed AML and MDS after allo-HCT
Study Duration:	
 
• Time from study opening to accrual completion – 18 months
 
• Time from accrual completion to primary data analysis – 3 months
 
• Total time from study opening to primary data analysis – 21 months
 
• Time from accrual completion to final data analysis (survival analysis) – 24 months
 
• Total time from study opening to final data analysis – 42 months
 

Participant Duration:	Patients will receive the investigational treatment for the first 28 days of the study (Cycle 1). Based on Day 28 response assessment, patients with CR/CRi will continue investigational treatment for another 28 days (Cycle 2); patients with SD or PR may also continue investigational treatment for another 28 days (Cycle 2) with permission by the investigator. All patients may receive a donor lymphocyte infusion (DLI) concurrent with flotetuzumab in either cycle, at the discretion of the treating physician and investigator; patients with PD at the end of Cycle 1 will come off study. All patients will be followed for 2 years after receiving investigational treatment.

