## 2.0 OBJECTIVES AND ENDPOINTS

Objectives	Endpoints
Primary	
To evaluate the efficacy of flotetuzumab in post-allo-HCT relapsed AML and MDS following Cycle 1 of flotetuzumab (Cycle 1 Day 28 assessment).	Efficacy assessed via composite endpoint of CR and CRi (Cycle 1 Day 28 assessment)
Secondary	

 
• To evaluate the efficacy of flotetuzumab monotherapy in post-allo-HCT relapsed AML and MDS following Cycle 2.
 
• To evaluate the safety and tolerability of flotetuzumab +/- DLI in the post-allo-HCT setting.
 
	
 
• Efficacy assessed at Cycle 2 Day 28 (or at C1 D28 in patients who receive only one cycle):               
 
○ Composite endpoint of CR and CRi at C2 D28
 
○ Overall Response (OR) Rate (defined as PR or greater)
 
○ Morphologic leukemia-free state (MLFS) Rate
 
○ Partial Response (PR) Rate
 
○ Stable Disease (SD) Rate
 
○ Progression Free Survival (PFS)
 
○ Overall Survival (OS)
 
 
 
• Safety and tolerability as assessed by:               
 
○ AE Grading per CTCAE v5.0
 
○ CRS & Neurotoxicity Grading per ASTCT Consensus Guidelines
 
○ Acute GVHD Grading per MAGIC criteria
 
○ Chronic GVHD Grading per NIH severity score
 
 
 

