## APPENDIX I: Study-Specific DSM Tables

Protocol Objectives and Subject Evaluability	
Objective	# of patients evaluable for this endpoint to date
Primary	
To evaluate the efficacy of flotetuzumab in post-allo-HCT relapsed AML and MDS following Cycle 1 of flotetuzumab (Cycle 1 Day 28 assessment).	
Secondary	
To evaluate the efficacy of flotetuzumab monotherapy in post-allo-HCT relapsed AML and MDS following Cycle 2 (or following Cycle 1 for patients that receive only one cycle).	CR and CRi at C2D28 = ORR = MLFS = PR = SD = PFS = OS =
To evaluate the safety and tolerability of flotetuzumab +/- DLI in the post-allo-HCT setting	AEs = CRS and neurotoxicity = Acute GVHD = Chronic GVHD =

Interim Analysis and Early Stopping Rules
Does the study design include an interim toxicity analysis? No
Does the study design include an interim futility analysis? Yes
If yes, please insert text describing interim futility analysis from the protocol Fifteen patients will be enrolled in the first stage. This cohort will include patients who withdraw from the study for reasons unrelated to drug toxicity. If at least 2 CR/CRi are observed out of the 15 patients, then an additional 10 patients will be enrolled. If 6 or more CR/CRi are observed at the end of study, we would conclude that there is evidence of efficacy to warrant further investigation. There is less than 5% chance to stop the trial at stage 1 if the “true” response is 30% or higher. Conversely, there will be 55% chance to terminate the study early if the true rate is only 10% or less.
If yes, please provide data from the interim futility analysis when completed:
Are there early stopping rules that outline circumstances under which the study must be suspended or closed? Yes
If yes, please insert text describing early stopping rules from the protocol A Bayesian sequential monitoring rule will be implemented for safety. The stopping rule is defined as $\Pr(\theta > \theta_T   \text{data}) > 0.8$ , where $\theta$ denotes the proportion of toxicities (as defined in Section 11.5) and $\theta_T$ denotes the expected serious toxicity rate for study treatments (set as $\theta_T = 20\%$ for non-GVHD toxicity and 25% for GVHD toxicity). Interval analyses will be performed

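### Section 5.5 makes the evaluable Cycle 2 Day 28 CR/CRi rate conditional on the Cycle 1 outcome, and the plan does not say which denominator leads

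*Combined protocol and SAP*

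**What the plan says.** In Section 5.5, the row for CR/CRi at C2D28 has two conditions. The first concerns treatment: "Have completed all Cycle 1 and 2 infusions of flotetuzumab", or stopped because of toxicity or progression. The second concerns assessment: "and undergone C2D28 disease assessment". The toxicity and progression exception sits inside the first condition. The second has no alternative.

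The next group of rows in the same table (ORR, MLFS, PR and SD rates) also asks for a C2D28 assessment, but adds a fallback: "or C1D28 assessment for patients who only received Cycle 1 treatment".

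Section 2.0 lists the secondary efficacy endpoints under a parent line: "Efficacy assessed at Cycle 2 Day 28 (or at C1 D28 in patients who receive only one cycle". The first item beneath it is "Composite endpoint of CR and CRi at C2 D28", and it is the only item that names its own time point. The DSM table in Appendix I words the objective as efficacy "following Cycle 2 (or following Cycle 1 for patients that receive only one cycle".

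On who reaches Cycle 2, the Protocol Summary says "patients with PD at the end of Cycle 1 will come off study". Section 5.2.2 sends CR/CRi patients on to Cycle 2, and PR/SD patients only with the investigator's permission.

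Section 11.7 plans both an ITT analysis (every patient given at least one dose) and a per-protocol analysis (evaluable patients). Section 11.8 describes an efficacy population of patients who completed at least one cycle or withdrew for possible toxicity, with no C2D28 condition. Section 10.0 measures PFS from first dose.

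**The concern.** Whether a patient has a C2D28 assessment depends largely on how Cycle 1 went. A denominator restricted to assessed patients leaves out known Cycle 1 failures and, through the permission step, is also shaped by judgement about SD and PR patients. The resulting rate answers a narrower question than how many treated patients are in CR/CRi after up to two cycles.

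There is also a coherence problem. CR/CRi is a subset of ORR, yet Section 5.5 gives the two rates different denominators, so the evaluable CR/CRi rate could exceed the evaluable ORR.

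PFS raises a related question. As the table reads in the text available, PFS falls in the group that needs a C1D28 or C2D28 assessment, and the any-infusion rule begins at OS. If so, a patient who dies before Day 28 is not evaluable for PFS, although that death is an event under Section 10.0.

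**Working it through.** **Plan's own figure.** The plan states no figure for the C2D28 endpoint. Its only related calculation is the primary C1D28 design in Sections 11.3 and 11.4: 15 + 10 patients, continue with at least 2 responses, 10% against 30%. Taking the final rule as Appendix I words it (at least 6 responses at the end of the study), the probability of a positive result is the sum over x₁ = 2,…,15 of P(X₁ = x₁)·P(X₂ ≥ 6 − x₁). This is 0.033 at 10% and 0.802 at 30%. The chance of stopping at stage 1 is 0.549 and 0.035. These match the stated alpha, power, 55% and less than 5%. None of this uses the C2D28 evaluability rule.

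**Who can be in the Section 5.5 denominator.**

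| C1D28 result | Route | C2D28 assessment possible? |
|---|---|---|
| CR/CRi | Cycle 2 by rule | Yes |
| PR or SD | Cycle 2 with permission | Only if permitted |
| PD | Off study | No |
| None (death or early stop in Cycle 1) | No Cycle 2 | No |

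Section 5.8 keeps early discontinuers in follow-up. However, follow-up is six-monthly and its marrow is taken only at suspected relapse or progression, so it does not supply a C2D28 assessment for someone who never started Cycle 2.

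**Size against all treated patients.** Let x be the CR/CRi patients at C2D28 and k the number assessed then. Assume 25 treated; replacement of unevaluable patients could make this larger. The Section 5.5 rate is x/k. The all-treated rate, with no C2D28 assessment counted as non-response, is x/25. The ratio is 25/k. The documents do not give k or x. Taking x = 6 for illustration, with exact 90% limits (Clopper-Pearson; the 90% level is from Section 11.7):

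| Denominator | Rate | 90% CI | Ratio to all treated |
|---|---|---|---|
| All 25 | 6/25 = 24% | 11–42% | 1 |
| k = 20 | 6/20 = 30% | 14–51% | 1.25 |
| k = 15 | 6/15 = 40% | 19–64% | 1.67 |
| k = 12 | 6/12 = 50% | 25–76% | 2.08 |

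**Size against the C1D28 fallback.** Let y be the patients without a C2D28 assessment who count as CR/CRi through their C1D28 result. The fallback rate is (x + y)/25. The Section 5.5 rate is higher when x/k > (x + y)/25, that is, when y < x(25 − k)/k.

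- k = 12, x = 6: the threshold is 6 × 13/12 = 6.5. With y = 2 the rates are 50% and 8/25 = 32%.
- k = 12, x = 2: the threshold is 2 × 13/12 = 2.2. With y = 4 the order reverses: 2/12 = 17% against 6/25 = 24%.

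Because CR/CRi patients are meant to go on to Cycle 2, y should usually be small. Upward bias is therefore the expected direction, but the rule does not guarantee it.

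**CR/CRi against ORR.** Suppose k = 12, x = 6, two further patients in PR, and all 25 evaluable for ORR through the fallback. Then evaluable CR/CRi is 6/12 = 50% and evaluable ORR is 8/25 = 32%.

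**The case against.** Four points on the other side have force.

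1. **An all-dosed analysis is already planned.** Section 5.5 feeds the per-protocol cohort, while the ITT cohort in Section 11.7 keeps Cycle 1 failures. A reader might infer that the published rate will describe only selected patients. The documents do not support that, since nothing says the per-protocol rate leads or stands alone. What remains is that nothing says the ITT rate leads, or how an ITT patient without a C2D28 assessment is counted. Section 11.8 adds a third population without reconciling it.

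2. **Section 2.0 is not unambiguous.** A reader might call Section 5.5 a flat contradiction of it. The CR/CRi item carries its own time point, so a rate among patients assessed at C2D28 is a possible reading. The tension is with the parent line, the Appendix I objective and the adjacent rows of Section 5.5.

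3. **Direction and size are not fixed.** The fallback comparison can reverse, and k is unknown. The 50% against 24% contrast is one assumed case; at k = 20 it is 30% against 24%.

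4. **The PFS point depends on a table split across a page.** The cell boundaries need confirming, and Section 10.0 excludes nobody. It is also tempting to apply the 2–4 month median survival without therapy (Section 1.1.1) to estimate deaths before Day 28. An exponential curve gives 15–27%. That median describes untreated patients; those here are treated and selected for performance status and organ function. The figure is not an estimate for this trial.

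The endpoints concerned are secondary and the analyses descriptive, which limits the stakes.

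**Conclusion.** The point holds in a limited form. The evaluable C2D28 CR/CRi rate under Section 5.5 is conditional on Cycle 1 outcome and lacks the C1D28 fallback that the Section 2.0 parent line, the Appendix I objective and the neighbouring response rows provide. Against all treated patients with unassessed counted as non-responders, it is higher by the factor 25/k whenever k is below 25 and at least one patient responds. This assumes 25 treated; k is not in the documents. Against the fallback rule, a higher rate is expected but not certain.

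The ITT analysis and the Section 11.8 population reduce the problem without closing it, because neither the leading analysis nor the handling of unassessed patients is stated. If the table reading is confirmed, the evaluable PFS set loses deaths before Day 28; how many cannot be derived from the documents. A reader might conclude that both features necessarily favour the drug in the published results. The plan does not establish that. The primary endpoint, sample size and stopping rules are untouched.

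**What to change.** In Section 5.5, and consistently in Sections 2.0, 11.7, 11.8 and Appendix I:

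- Define the leading C2D28 CR/CRi rate over all patients who received any flotetuzumab. Use the C1D28 result for patients who had only one cycle, and count patients with no qualifying assessment as non-responders.
- Report the rate among patients assessed at C2D28 only as a supplement, labelled as conditional on reaching that assessment.
- Confirm the cell boundaries of the evaluability table, and place PFS with OS so that any infusion makes a patient evaluable.

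This needs no extra patients, visits or procedures. The cost is an edit to five places and, in all likelihood, a less favourable secondary rate.
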